1. INTRODUCTION

This document describes the rules and conventions to be used in the presentation and analysis of safety and immunogenicity data at interim and final analyses for Protocol 216152 (H08_01TP). It describes the data to be summarized and analyzed, including specifics of the statistical analyses to be performed. This statistical analysis plan (SAP) is based on Original Protocol dated 27 April 2022, Protocol Amendment 1 dated 15 August 2022, and Protocol Amendment 2 dated 08 June 2023. In scope of this analysis are all primary and secondary objectives and part of tertiary CCI. The iSRC/SRT analyses will be described in a separate document.

2. STUDY OBJECTIVES

2.1. PRIMARY OBJECTIVE

[figure not shown]
To evaluate the safety and reactogenicity profile of GSK Vaccines Institute for Global Health (GVGH) invasive nontyphoidal Salmonella-typhoid conjugate vaccine (iNTS-TCV) in healthy European/African adults.

2.2. SECONDARY OBJECTIVES

- To evaluate the long-term safety profile of GVGH iNTS-TCV vaccine in healthy European/African adults
- To evaluate the immunogenicity profile of GVGH iNTS-TCV vaccine in healthy European adults
- To evaluate the seroresponse with the GVGH iNTS-TCV vaccine after each study intervention administration in healthy European adults
- To evaluate the immunogenicity profile of GVGH iNTS-TCV vaccine in healthy African adults
- To evaluate the seroresponse with the GVGH iNTS-TCV vaccine after each study intervention administration in healthy African adults

2.3. TERTIARY OBJECTIVES

CCI

Document: \\dccar2dnetvnasc01p-lan1.quintiles.net\cp_ops\PROJECTS\Glaxo SmithKline\GSK216152_WZA10802\SAP
Author: PPD Version Number: 2.0
Version Date: 07DEC2023

Template No: CS_TP_BS016 – Revision 7
Effective Date: 01Nov2021

Reference: CS_WI_BS005

3. STUDY DESIGN

[figure not shown]
3.1. GENERAL DESCRIPTION

This is a Phase 1/2a, observer-blind, randomized, dose-escalation, controlled, multi-country, two-staged, and staggered study including 9 groups.

The study will be conducted overall (both Stage 1 and Stage 2) with approximately 155 healthy adult participants (18 to 50 years of age). The healthy European adults will be randomly assigned to 1 of the groups indicated for Stage 1. The healthy African adults will be randomly assigned to 1 of the groups indicated for Stage 2. Each group will receive 2 of the 11 study interventions at each administration, except for the Control group in Stage 2 which will receive 4 study interventions (a different active comparator at each administration time point together with saline).

Each participant will receive 1 randomly selected intramuscular study intervention per arm on Day 1, Day 57, and Day 169.

Figure 1 Study Schema

Stage 1

Stage 1 (Europe) will follow a 2-step staggered design, leading in with low doses of all the study interventions, in a dose-escalation manner. The sentinel approach will be followed for the first 10 participants each in Step 1 and Step 2, in which only 1 participant will be treated daily. This will be

Document:	\\dccar2dnetvnasc01p-lan1.quintiles.net\cp_ops\PROJECTS\Glaxo SmithKline\GSK216152_WZA10802\SAP
Author:	PPD

Version Number: 2.0
 Version Date: 07DEC2023

Template No: CS_TP_BS016 – Revision 7
 Effective Date: 01Nov2021

Reference: CS_WI_BS005

done in order to ensure maximum safety of the participants.

In Step 1, 10 healthy European adults, randomized in a 2:2:1 ratio, will receive:

- The low dose of the candidate iNTS-TCV vaccine and concomitant saline to be administered in different arms (Study Group 1), or
- Separate administration of low doses of iNTS-GMMA and TCV vaccines in different arms (Study Group 2), or
- Placebo and saline in different arms (Study Group 3).

The 10 sentinel participants in Step 1 will receive the first study intervention on consecutive days and a telephonic safety follow-up call will be performed on the next day. If the participants have any complaints, they will be invited to the study site for an evaluation of the possible adverse events (AEs) and holding rules, prior to administration of study intervention in the next participant. If the Investigator becomes aware of a holding rule being met, he/she must suspend administration of the study intervention and inform the Sponsor's delegate immediately who will in-turn inform the Sponsor.

The internal Safety Review Committee (iSRC) will review all safety data collected up to 7 days after the first study intervention in Step 1. Step 2 will only commence if there is a favorable safety assessment during this review.

In Step 2, 40 healthy European adults will be randomized in a 2:2:1 ratio. A staggered approach will be followed for the first 10 sentinel participants and these participants will be followed up with a safety follow-up call on the next day of administration of study intervention. If the participants have any complaints, they will be invited to the study site for an evaluation of the AEs and holding rules, prior to administration of study intervention in the next participant. If the Investigator becomes aware of a holding rule being met, he/she must suspend administration of the study intervention and inform the Sponsor's delegate immediately who will in-turn inform the Sponsor. The remainder of the 30 participants will receive the study intervention in a sequential (at least 60 minutes apart) manner. The participants in Step 2 will receive:

- The full dose of the candidate iNTS-TCV vaccine and concomitant saline to be administered in different arms (Study Group 4), or
- Separate administration of full doses of iNTS-GMMA and TCV vaccines in different arms (Study Group 5), or

Placebo and saline in different arms (Study Group 6).

For the trial to proceed to Stage 2, a favorable evaluation of all available safety data by the iSRC following the first and second study intervention administrations (up to 28 days after second administration) in Step 2 of Stage 1 will be required. In case a No-Go decision is made, the study will be terminated at the end of Stage 1 and there will be no further administration of the study intervention in Step 2.

Stage 2

Document: \\dccar2dnetvnasc01p-lan1.quintiles.net\cp_ops\PROJECTS\Glaxo SmithKline\GSK216152_WZA10802\SAP
Author: PPD Version Number: 2.0
Version Date: 07DEC2023

Template No: CS_TP_BS016 – Revision 7
Effective Date: 01Nov2021

Reference: CS_WI_BS005

In Stage 2 (Africa), a total of 105 healthy African adults, randomized in a 3:3:1 ratio, will receive:

- The full dose of the candidate iNTS-TCV vaccine and concomitant saline to be administered in different arms (Study Group 7), or
- Separate administration of full doses of iNTS-GMMA and TCV vaccines in different arms (Study Group 8), or
- MenACWY (Menveo) and saline for the first administration, TdaP (Boostrix) and saline for the second administration and Typhoid Vi polysaccharide vaccine (Typhim Vi) and saline for the third administration in different arms (Study Group 9). This is the Control_Stage 2 Group.

The first 21 participants in Stage 2 will initially be recruited with administration proceeding sequentially, at least 60 minutes apart. All safety data from these participants up to 7 days after the first administration of the study intervention will be reviewed by the iSRC and the recruitment of the remaining 84 participants in Stage 2 will only commence if there is a positive evaluation by the iSRC. The study interventions will be administered in parallel in the remaining 84 participants.

All 155 participants (Stage 1 and Stage 2) will be closely observed for a minimum of 60 minutes after each study intervention administration, before leaving the facilities. The Investigator will decide if the participant should be observed for more than 60 minutes after each study intervention administered, if required.

An internal GSK Safety Review Team (SRT) and iSRC will also be involved in the safety oversight for this study. For all planned safety data reviews refer to Table 14 and 15 of the study protocol.

The trial will be conducted in 2 sites, each with a different Principal Investigator. A total of 155 participants are planned to be randomized to achieve at least 133 evaluable participants. Each participant will be part of this trial for approximately 13 months (from the Screening starting 28 days before first study intervention administration and until 6 months after third study intervention administration).

Document: \\dccar2dnetvnasc01p-lan1.quintiles.net\cp_ops\PROJECTS\Glaxo SmithKline\GSK216152_WZA10802\SAP
Author: PPD Version Number: 2.0
Version Date: 07DEC2023

Template No: CS_TP_BS016 – Revision 7
Effective Date: 01Nov2021

Reference: CS_WI_BS005

Table 2 Intervals Between Study Visits

Interval	Planned visit interval	Allowed interval range
Screening (Day -28) → Visit 1 (Day 1)	Up to 28 days*	Up to 28 days*
Visit 1 (Day 1) → Visit 2 (Day 8)	7 days	7-10 days
Visit 1 (Day 1) → Reminder Phone Call 1 (Day 4)	3 days	1-3 days
Visit 1 (Day 1) → Visit 3 (Day 29)	28 days	28-33 [#] days**
Visit 1 (Day 1) → Visit 4 (Day 57)	56 days	52-62 days**
Visit 4 (Day 57) → Visit 5 (Day 64)	7 days	7-10 days
Visit 4 (Day 57) → Reminder Phone Call 2 (Day 60)	3 days	1-3 days
Visit 4 (Day 57) → Visit 6 (Day 85)	28 days	28-33 [#] days**
Visit 4 (Day 57) → Visit 7 (Day 169)	112 days	110-126 days**
Visit 4 (Day 57) → Visit 7 (Day 169)	112 days	110-140 [§] days**
Visit 7 (Day 169) → Visit 8 (Day 176)	7 days	7-10 days
Visit 7 (Day 169) → Reminder Phone Call 3 (Day 172)	3 days	1-3 days
Visit 7 (Day 169) → Visit 9 (Day 197)	28 days	28-33 [#] days**
Visit 7 (Day 169) → Visit 10 (Day 337)	168 days	154-182 days

*Screening evaluations may be completed up to 28 days before Visit 1 (Day 1). Site staff should allow enough time between the Screening Visit and Visit 1 to receive and review hematology/biochemical results. If screening laboratory tests are performed within 3 days of vaccination, it would not be necessary to repeat them pre-vaccination for the first study intervention administration.

**Visits out of the allowed interval can lead to elimination from the Per Protocol Set for analysis of immunogenicity.

[§] Interval range will only be applicable for Stage 2 participants in Malawi.

#Under special circumstances, e.g., during coronavirus disease 2019 pandemic, the length of interval between visits for the collection of biological samples or for the vaccine administration may be extended to 38 days.

3.2. SCHEDULE OF EVENTS

Schedule of events can be found in Section 1.3, Table 1 of the protocol.

3.3. CHANGES TO ANALYSIS FROM PROTOCOL

Entered Set is defined in Section 5 to comprise of participants who provide informed consent for the

Document: \\dccar2dnetvnasc01p-lan1.quintiles.net\cp_ops\PROJECTS\Glaxo SmithKline\GSK216152_WZA10802\SAP
 Author: PPD Version Number: 2.0
 Version Date: 07DEC2023

Template No: CS_TP_BS016 – Revision 7
 Effective Date: 01Nov2021

Reference: CS_WI_BS005

study.

4. PLANNED ANALYSES

4.1. INTERNAL SAFETY REVIEW COMMITTEE (iSRC)

This study will be overseen by an iSRC operating under a charter. Please refer to iSRC charter for details. An iSRC will be established to monitor the safety of participants throughout the trial and, more specifically, to recommend whether proceeding from low dose in Stage 1/Step 1 to the full dose in Stage 1/Step 2 is permissible, based on the accumulated safety data. They will also recommend proceeding the clinical testing of the vaccine in African participants in Stage 2 based on the post-primary safety results in Stage 1 (iSRC #3).

4.2. SAFETY REVIEW TEAM (SRT)

Instream blinded monitoring will also be performed by the internal GSK Safety Review Team (SRT). Refer the iSRC charter for details.

4.3. INTERIM ANALYSIS

A group-unblinded interim analysis will be performed for all immunogenicity data accumulated up to 28 days after second intervention (Day 85) administration in Stage 2. At this point, the statistical team at IQVIA will be unblinded for the analysis (i.e., will have access to individual participant treatment assignments). The remaining study personnel will stay blinded (i.e., will not have access to the individual participant treatment assignment) until Day 197. It is possible however, due to limited sample size, that indirect unblinding occurs for a few participants having as specific demographic characteristics or protocol deviations (e.g., participant with max height or weight, protocol deviations occurring only in a single group). Therefore, anyone having access to the analysis of Day 85 could become unblinded regarding those specific cases. The study will be considered as a single-blind from this point onwards. Results from immunogenicity analysis in Stage 2, and if applicable, in participants receiving the full dose in Stage 1/Step 2 will help with the design and approach in subsequent studies. No individual listings or data with the participants identifying information will be disseminated. The investigators and the participants will not have access to the treatment allocation up to study end (Day 337).

All analyses are descriptive and with the aim to characterize the safety and immunogenicity data and therefore no statistical adjustment for interim analysis is required.

Derivations and definitions for the interim analyses will be based on those required for the final analysis contained in this analysis plan, unless deviations are stated within the text.

Document:	\dccar2dnetvnasc01p-lan1.quintiles.net\cp_ops\PROJECTS\Glaxo SmithKline\GSK216152_WZA10802\SAP		
Author:	PPD	Version Number:	2.0
		Version Date:	07DEC2023

Template No: CS_TP_BS016 – Revision 7
Effective Date: 01Nov2021

Reference: CS_WI_BS005

Tables presenting summary statistics planned for final analysis to be generated at the time of interim analyses are listed in the document with table shells (see “Interim Analysis”). No unblinded individual participant listings or tables will be generated at the time of interim analyses.

Comparative analyses will be exploratory and should be interpreted with caution considering that there is no adjustment for multiplicity and that study is not powered for such comparisons.

4.4. FINAL ANALYSIS

All final, planned analyses identified in this SAP will be performed by IQVIA Biostatistics following sponsor authorization of this Statistical Analysis Plan, database lock, and unblinding of treatment.

After unblinding of the Sponsor personnel (partial observer-blind), an analysis on all data up to and including Day 197 (Visit 9) will be performed and individual listings will be generated.

A final CSR will be produced after the analysis after Visit 9 in Stage 2.

4.5. EXTENDED SAFETY FOLLOW-UP ANALYSIS

Data collected during the extended safety follow-up period will be analyzed after Day 337 and the analysis after Day 337 will be included in an integrated CSR to be written after.

5. ANALYSIS SETS

5.1. ENTERED SET

Participants who provided informed consent.

5.2. ENROLLED SET

Participants who provided informed consent and were randomized or received study intervention or underwent a post-screening procedure. The allocation in a group is based on the administered intervention.

Note: Participants who never passed screening even if rescreened (screening failures) and participants screened but never enrolled into the study (met eligibility but not needed for the study) are excluded from the Enrolled analysis set.

Document: \\dccar2dnetvnasc01p-lan1.quintiles.net\cp_ops\PROJECTS\Glaxo SmithKline\GSK216152_WZA10802\SAP
Author: PPD Version Number: 2.0
Version Date: 07DEC2023

Template No: CS_TP_BS016 – Revision 7
Effective Date: 01Nov2021

Reference: CS_WI_BS005

5.3. EXPOSED SET (ES)

All participants who received at least 1 dose of the study intervention. The allocation in a group is based on the administered intervention.

5.3.1. UNSOLICITED SAFETY SET

All participants who received at least 1 dose of the study intervention (ES) that report unsolicited adverse events (AEs)/report not having unsolicited AEs. The allocation in a group is based on the administered intervention.

Note: Participants will be considered to have reported no unsolicited AEs if they are in the study 28 days after vaccination without providing AEs.

5.3.2. SOLICITED SAFETY SET

All participants who received at least 1 dose of the study intervention (ES) who have solicited safety data for that intervention. The allocation in a group is based on the administered intervention.

5.4. FULL ANALYSIS SET (FAS)

All participants who received at least 1 dose of the study intervention and have post-dose immunogenicity data. The allocation in a group is based on the randomized intervention. The FAS for immunogenicity will be defined by time point.

The Full Analysis Set will be used as second-line analysis for secondary and tertiary endpoints if the percentage of vaccinated participants (in any study group at any time point) with serological results excluded from the Per-protocol Set for analysis of immunogenicity is 10% or more.

5.5. PER-PROTOCOL SET (PPS)

All eligible participants who received all doses as per protocol, had immunogenicity results post-dose, complied with dosing/blood draw intervals, without intercurrent conditions that may interfere with immunogenicity, without prohibited concomitant medication/vaccination and without protocol deviation leading to exclusion. The PPS for immunogenicity will be defined by time point.

The protocol deviations leading to exclusion of the participants are described in Section 11.2. Three Per-protocol Sets for analysis of immunogenicity will be derived:

Document: \\dccar2dnetvnasc01p-lan1.quintiles.net\cp_ops\PROJECTS\Glaxo SmithKline\GSK216152_WZA10802\SAP
Author: PPD Version Number: 2.0
Version Date: 07DEC2023

Template No: CS_TP_BS016 – Revision 7
Effective Date: 01Nov2021

Reference: CS_WI_BS005

5.5.1. PER-PROTOCOL SET FOR ANALYSIS OF IMMUNOGENICITY AT DAY 29

The analysis set will contain all participants included in the Per-protocol Set, with no protocol deviations leading to exclusion until Day 29 and with at least 1 valid immunogenicity data available at Day 29.

5.5.2. PER-PROTOCOL SET FOR ANALYSIS OF IMMUNOGENICITY AT DAY 85

The analysis set will contain all participants included in the Per-protocol Set, with at least 1 immunogenicity data available at Day 85 without any protocol deviations that could lead to exclusion.

5.5.3. PER-PROTOCOL SET FOR ANALYSIS OF IMMUNOGENICITY AT DAY 197

The analysis set will contain all participants included in the Per-protocol Set with at least 1 immunogenicity data available at Day 197 without any protocol deviations that could lead to exclusion.

Analyses will be performed on specific sets as per the table below.

Analysis	Entered Set	Enrolled Set	Exposed Set	Un-solicited Safety Set	Solicited Safety Set	Full Analysis Set**	Per-protocol (PP) Set		
							PP Set	PP Set	PP Set
							Day 29	Day 85	Day 197
Participant Disposition	✓								
Baseline Assessments		✓	✓				✓	✓	✓
Concomitant Medications			✓						
Exposure			✓						
Immunogenicity Analysis						✓	✓	✓	✓
Protocol Deviations			✓						
Solicited Adverse Events					✓				
Unsolicited Adverse Events				✓					
Solicited and Unsolicited Adverse Events			✓						
Other Safety (lab, vitals)			✓						

** Analysis in this set will be performed if the percentage of vaccinated participants with serological results excluded from the Per-protocol Set for analysis of immunogenicity is 10% or more

Document: \\dccar2dnetvnasc01p-lan1.quintiles.net\cp_ops\PROJECTS\Glaxo SmithKline\GSK216152_WZA10802\SAP
 Author: PPD Version Number: 2.0
 Version Date: 07DEC2023

Template No: CS_TP_BS016 – Revision 7
 Effective Date: 01Nov2021

Reference: CS_WI_BS005

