11.2. DEVIATIONS RELATED TO IMMUNOGENICITY ANALYSIS

Changes to the procedures or events, which may impact the quality of the immunogenicity data, will be considered important protocol deviations and will be described within the clinical study report. These changes or events will include any circumstances that will alter the evaluation of the immunogenicity results. Examples include, but may not be limited to, sample processing errors that lead to inaccurate immunogenicity results, and/or inaccurate dosing.

Participants may be eliminated from the per-protocol set for analysis of immunogenicity if, during the study, they incur a condition that has the capability of altering their immune response or are confirmed to have an alteration of their initial immune status. Participants may also be eliminated

Document: \\dccar2dnetvnasc01p-lan1.quintiles.net\cp_ops\PROJECTS\Glaxo SmithKline\GSK216152_WZA10802\SAP
Author: PPD Version Number: 2.0
Version Date: 07DEC2023

Template No: CS_TP_BS016 – Revision 7
Effective Date: 01Nov2021

Reference: CS_WI_BS005

from the per-protocol set as described in Section 7.2 and Section 9.3 of the protocol. Such scenarios will be discussed by the study team and decision to exclude a participant and/or data from the Per-protocol analysis set (Day 29, Day 85 and Day 197) will be taken on a case-by-case basis.

Other deviations (not a comprehensive list) leading to elimination from the per-protocol set are:

- invalid informed consent
- fraudulent data
- randomization code broken
- dose volume insufficient
- vaccination not according to protocol
- vaccine dose storage conditions (temperature deviation)
- vaccine administered out of expiry date
- violation of inclusion/exclusion criteria
- interval between doses
- interval between post vaccination blood sampling and previous dose
- two doses not in the same treatment group
- concomitant infection related to study vaccine or not related to study vaccine that may alter the immune response
- serology result at post vaccination dose 2 not available for all assays (blood sample not available or result not available)

Protocol Deviation Management Plan (PDMP) describes the complete list of elimination codes that could lead to exclusion from the per-protocol set.

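### The dated per-protocol sets in SAP 5.5 inherit whole-study conditions, and the missing dose-2 serology exclusion in SAP 11.2 is not limited to Day 85

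*SAP*

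**What the plan says.** SAP 5.5 describes the PPS as "All eligible participants who received all doses as per protocol, had immunogenicity results post-dose, complied with dosing/blood draw intervals", free of interfering conditions, prohibited treatment and excluding deviations. The paragraph closes with "The PPS for immunogenicity will be defined by time point". Protocol Table 10 has the same definition and the same closing statement.

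Three dated sets follow. SAP 5.5.1 (Day 29) reads "The analysis set will contain all participants included in the Per-protocol Set, with no protocol deviations leading to exclusion until Day 29" and asks for at least one valid Day 29 result. SAP 5.5.2 (Day 85) also starts from participants in the PPS, "with at least 1 immunogenicity data available at Day 85 without any protocol deviations that could lead to exclusion". SAP 5.5.3 (Day 197) repeats that form for Day 197. Neither 5.5.2 nor 5.5.3 has a time limit.

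SAP 11.2 lists further deviations that lead to elimination from the per-protocol set. One is "serology result at post vaccination dose 2 not available for all assays (blood sample not available or result not available". No day is attached, and the printed list has no matching item for dose 1 or dose 3. The same section lets the study team decide case by case whether to "exclude a participant and/or data from the Per-protocol analysis set (Day 29, Day 85 and Day 197". It adds that a separate Protocol Deviation Management Plan (PDMP) "describes the complete list of elimination codes that could lead to exclusion from the per-protocol set".

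For the Day 85 interim, SAP 4.3 states: "Derivations and definitions for the interim analyses will be based on those required for the final analysis contained in this analysis plan", apart from deviations given in the text. None is given for the PPS.

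**The concern.** The PPS is the main immunogenicity set, so its membership at each visit should follow from the SAP alone. Here the stated principle (by time point) and the construction (subsets of a whole-study set) give different answers, and the dose-2 item has no visit attached.

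Three things are at stake. First, a participant with a valid Day 197 result can be dropped because the Day 85 sample failed. Protocol 9.2 names Stage 2 Day 197 as the comparison the sample size was chosen for. Second, someone whose dose 3 is withheld under Protocol 7.2, and who is encouraged to continue other procedures, can lose valid Day 29 and Day 85 results because of a later event. Third, the same visit can have different participants at the interim and at the final analysis, because the all-doses condition can be settled for everyone only at the final analysis.

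**Working it through.** **Step 1: the text side by side.**

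| Set | Starts from the PPS (all doses, no excluding deviation)? | Own time limit | Result required |
|---|---|---|---|
| Day 29 (5.5.1) | yes | until Day 29, on deviations only | at least 1 at Day 29 |
| Day 85 (5.5.2) | yes | none | at least 1 at Day 85 |
| Day 197 (5.5.3) | yes | none | at least 1 at Day 197 |

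Read literally, the limit in 5.5.1 does nothing, because the parent set has already removed anyone with a later excluding deviation or a missed dose. The absence of a limit in 5.5.3 matters little, since Day 197 is the last immunogenicity sample. The dose-2 item does matter there: it acts on the parent set, and 5.5.3 inherits the removal. Dose 3 is planned for Day 169, so at the Day 85 interim the all-doses condition is undetermined for anyone not yet at dose 3.

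The wording on assays is also open. It can mean any assay missing or every assay missing. The first conflicts with the single result that 5.5.2 accepts; the second agrees with it.

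**Step 2: the plan's own figure.** Protocol 9.2 gives 155 randomized, 12% dropout per group and at least 133 evaluable. Rounding 0.88 × n down for groups of 4, 4, 2, 16, 16, 8, 45, 45 and 15 gives 3 + 3 + 1 + 14 + 14 + 7 + 39 + 39 + 13 = 133. It reproduces, with 39 of 45 in each large Stage 2 arm.

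**Step 3: Day 29, literal reading.** The documents do not say when the 12% is lost. If all losses fall before Day 29, the two readings agree and 0 valid results are lost. If all 6 (45 − 39) fall between Day 29 and dose 3, 6 of 45 (13.3%) are lost. Participants lost after dose 3 have had all doses, so that condition does not remove them.

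For two arms of m with a common SD, the half-width of the 95% CI for the log GMC ratio is proportional to w(m) = t(0.975; 2m − 2) × √(2/m). Then w(45) = 0.419, w(39) = 0.451, and w(39)/w(45) = 1.077. The range is 0 to 7.7% wider.

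**Step 4: Day 197, dose-2 item as written.** Assume k of the 39 evaluable per arm lack the Day 85 result.

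| k | k/39 | w(39 − k)/w(39) | CI wider by |
|---|---|---|---|
| 0 | 0% | 1.000 | 0% |
| 1 | 2.6% | 1.014 | 1.4% |
| 2 | 5.1% | 1.028 | 2.8% |
| 4 | 10.3% | 1.058 | 5.8% |

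The model in SAP 15 uses full-dose groups from both stages. With 14 + 39 = 53 per arm, the same formula gives 1.0%, 2.0% and 4.1% for k = 1, 2 and 4. The repeated-measures model itself is not reproduced here.

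**Step 5: does the Full Analysis Set (FAS) cover it?** The second-line FAS analysis runs when exclusions reach 10% in any group at any time point. That takes 1 of 4, 1 of 10 (pooled placebo, as SAP 6.2 groups it), 2 of 15 or 16, or 5 of 45. With independent exclusions at one rate p, the chance that some group triggers is 1 − ∏ P(X ≤ c − 1), where X is binomial (n, p) and c is the count needed in that group.

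| p | Groups 4, 4, 10, 16, 16, 45, 45, 15 | Stage 2 groups only (45, 45, 15) |
|---|---|---|
| 2.6% | 49% | 7% |
| 5% | 81% | 29% |
| 8.9% | 98% | 76% |

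The largest losses above (6/45 and 4/39) reach 10% in their own arm and bring in the FAS. Small losses confined to Stage 2 often would not.

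**The case against.** The best answer is that nobody would program the literal reading. The time-point sentence closes the same paragraph as the definition and can be read as governing it. The SAP derives three dated sets, and its table of analyses has no column for an undated PPS. The literal reading empties the limit in 5.5.1 of meaning and leaves the planned interim without a determinable PPS for some participants. Protocol 9.3 says participants meeting the Protocol 7.2 criteria may be eliminated, and SAP 11.2 makes that a case-by-case decision across the three sets. The 11.2 list is declared incomplete, and the PDMP may assign codes by visit.

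Much of this stands: the visit-specific reading is probably intended. But the discretionary wording does not soften the all-doses condition, which is part of the definition, nor the list of other deviations, which are said to lead to elimination. The SAP has no rule tying a deviation to a dated set.

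A reader might also infer that the reading would be chosen by people who know the assignments, since the IQVIA statistical team is unblinded for the interim. The documents do not support that. SAP 11.2 gives exclusion decisions to the study team, and SAP 4.3 keeps personnel other than the IQVIA statistical team blinded until Day 197. Either reading would also apply to both arms alike.

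**Conclusion.** The wording defect is real, with moderate confidence as to its practical effect because the PDMP was not available. The firmer part is the dose-2 item: as written, and combined with 5.5.3, it removes participants with valid Day 197 results. The nesting in 5.5.1 to 5.5.3 is better described as a conflict between stated principle and construction. It would be a mistake to conclude that the Day 85 set will be empty, or that Day 29 results will certainly be lost; that follows only if the literal text is programmed.

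The size is small: 0 to 6 of 45 Day 29 results per large Stage 2 arm, with the maximum only if all losses fall between Day 29 and dose 3, and intervals up to about 8% wider at Day 29 and 0 to 6% at Day 197. These figures rest on assumed timing and counts and a simple two-sample interval. No hypothesis is tested, between-group comparisons are exploratory and unpowered, the primary safety objective uses other sets, and the FAS analysis is added once exclusions reach 10%. The change is worth making because it is cheap, not because a conclusion of the trial depends on it.

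**What to change.** Replace the nested definitions with one rule. PPS at Day X contains eligible participants who received all doses due before Day X as planned, met the dose and blood-draw intervals up to and including Day X, had no excluding condition, treatment or deviation up to and including Day X, and have at least one valid immunogenicity result at Day X.

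Limit the dose-2 serology item in SAP 11.2 to the Day 85 set. State whether it means any or every assay missing; every assay missing would agree with the single result that 5.5.2 accepts. Use the same definitions at the interim and final analyses, and align the PDMP codes so that each names the set or sets it affects.

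The cost is a few lines of SAP text, the matching derivation code and a check of the PDMP. The number analysed will vary slightly by visit, which the tables should show.
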